Interscalene Block versus Superior Trunk Block: A Randomized Controlled Clinical Trial

FUNDER: Research & Education Fund, Department of
Anesthesiology, Critical Care & Pain
Management

PROTOCOL NO.: IRB#2017-0979

VERSION & DATE: 12/3/19

PROTOCOL SYNOPSIS

| | |
|--------------------------------|--|
| Protocol Title: | Interscalene Block versus Superior Trunk Block: A Randomized Controlled Clinical Trial |
| Protocol Number: | 2017-0979 |
| Protocol Date: | 7/3/2019 |
| Sponsor: | N/A |
| Principal Investigator: | [name] |
| Products: | N/A |
| Objective: | Sparing the phrenic nerve by administering ultrasound-guided low volume superior trunk block (STB) and interscalene block (ISB) for arthroscopic shoulder surgery. |
| Study Design: | Randomized Controlled Trial |
| Enrollment: | 126 total |
| Subject Criteria: | 
 • Patients who will be undergoing arthroscopic primary unilateral labral repair/stabilization of the shoulder, arthroscopic shoulder rotator cuff repair, and arthroscopic shoulder • capsular release, labral debridement, and bankart repair • Age 18 to 80 years • Planned use of general anesthesia and interscalene or superior trunk block • Ability to follow study protocol • English speaking • ASA I - III |
| Study Duration: | 
 • 9/2017- 8/2018 |
| Data Collection: | 
 • Demographics • Respiratory Parameters (MV, RR, TV) • Diaphragm Analysis • Patient Satisfaction • Incidence of Adverse Effects (horner's/hoarseness, dyspnea, hiccups, coughing) • Pulm Function (NIF, FEV1, FVC) • Sensory Exam • Handgrip • NRS pain scores at rest, at movement • Opioid Consumption • Neuropraxia |

| | |
|-------------------------------------|--|
| | 
 • Nerve Block Success • Length of PACU stay • Blinding assessment • Time to meet discharge criteria |
| 
Outcome Parameters:
 | 
 1. Our primary outcome will be the incidence of hemidiaphragmatic paralysis (HDP) with superior trunk block and interscalene blocks as measured by ultrasound before and after the surgery as well as NRS Pain scores at rest in the PACU measured after the surgery every 30 minutes where worst pain in PACU will be the highest recorded number during PACU stay. 2. Full resolution of the block will be reported by the patient on POD 1 via RA phone call 3. Handgrip as measured by dynamometer. Maximum grip strength will be assessed pre op and upon 60 min after PACU arrival (2 measurements will be done per time point and the average will be recorded) 4. Change in respiratory function as measured by changes in average minute ventilation, respiratory rate and tidal volume from preoperative baseline using a non-invasive monitoring device, and by changes in forced maneuvers: NIF, FEV1 and FVC measured preoperatively in holding area and 60 minutes postoperatively in the PACU. 5. incidence of ISB related side effects: horner's syndrome, hoarseness, hiccups, coughing, dyspnea in PACU 6. Time to readiness for PACU discharge (time of PACU admission to time of readiness to discharge, measured by Post Anesthetic Discharge Scoring System) evaluated every 15 minutes. 7. Block duration 8. Incidence of paresthesia / neuropraxia (POD1, POD 2): persistent tingling, numbness in POD1, if patient reports persistent neuropraxia after POD2, will follow up on POD7. If persists, will notify attending anesthesiologist and continue to follow until postoperative neurologic symptoms (PONS) resolves. 9. NRS Pain Scores at rest and with movement (PACU, POD 1, POD2) 10. Opioid consumption (PACU, POD1, POD2) |
| 
Statistical Analysis:
 | 
Proposed analysis (e.g., student's t-test, ANOVA, chi-square, regression, etc.): Non-inferiority and superiority tests
 
 2. Alpha level: 0.025 3. Beta or power level: 80% |

| | |
|--|--|

2.0 PRODUCT DESCRIPTION

N/A

3.0 OBJECTIVE OF CLINICAL STUDY

1. Does the Superior trunk block spare the phrenic nerve more often than the ISB?
2. Does the Superior trunk block provide as adequate analgesia as an ISB for shoulder arthroscopy?
3. Does the Superior trunk block spare motor blockade of the hand?
4. Does the Superior trunk block spare the recurrent laryngeal nerve, preventing hoarseness more often than the ISB?

4.0 STUDY HYPOTHESES

1. The superior trunk block spares the phrenic nerve more often than the ISB.
2. Forced respiratory maneuvers (negative inspiratory force (NIF), FEV1, and FVC) will be spared with the STB in comparison to the ISB.
3. STB will be noninferior to the ISB with respect to worst NRS pain score at rest in the PACU

5.0 STUDY DESIGN

5.1 Study Duration

9/2017 – 8/2018

5.2 Endpoints

5.2.1 Primary Endpoint

- Our primary outcome will be the incidence of hemidiaphragmatic paralysis (HDP) with superior trunk block and interscalene blocks as measured by ultrasound before and after the surgery as well as NRS Pain scores at rest in the PACU measured after the surgery every 30 minutes where worst pain in PACU will be the highest recorded number during PACU stay.

5.2.2 Secondary Endpoints

- Full resolution of the block will be reported by the patient on POD 1 via RA phone call
- Handgrip as measured by dynamometer. Maximum grip strength will be assessed pre op and upon 60 min after PACU arrival (2 measurements will be done per time point and the average will be recorded)
- Change in respiratory function as measured by changes in average minute ventilation, respiratory rate and tidal volume from preoperative baseline using a non-invasive monitoring device, and by changes in forced maneuvers: NIF, FEV1 and FVC measured preoperatively in holding area and 60 minutes postoperatively in the PACU.
- incidence of ISB related side effects: horner's syndrome, hoarseness, hiccups, coughing, dyspnea in PACU
- Time to readiness for PACU discharge (time of PACU admission to time of readiness to discharge, measured by Post Anesthetic Discharge Scoring System) evaluated every 15 minutes.
- Block duration
- Incidence of paresthesia / neuropraxia (POD1, POD): persistent tingling, numbness in POD1, if patient reports persistent neuropraxia after POD2, will follow up on POD7. If persists, will notify attending anesthesiologist and continue to follow until postoperative neurologic symptoms (PONS) resolves.
- NRS Pain Scores at rest and with movement (PACU, POD 1, POD2)
- Opioid consumption (PACU, POD1, POD2)

5.3 Study Sites

Hospital for Special Surgery Main Hospital – Ambulatory Surgery

6.0 STUDY POPULATION

6.1 Number of Subjects

126 subjects

6.2 Inclusion Criteria

Subjects of either gender will be included if they:

1. Patients who will be undergoing arthroscopic primary unilateral labral repair/stabilization of the shoulder, arthroscopic shoulder rotator cuff repair, and arthroscopic shoulder
2. capsular release, labral debridement, and bankart repair
3. Age 18 to 80 years
4. Planned use of general anesthesia and interscalene or superior trunk block
5. Ability to follow study protocol
6. English speaking
7. ASA I - III

6.3 Exclusion Criteria

Subjects will be excluded from the study if they:

1. Pre-existing neuropathy of the operative limb
2. Younger than 18 years old and older than 80
3. Patients with severe respiratory disease
4. Allergy to one of the study medications
5. Chronic gabapentin/pregabalin use (regular use for longer than 3 months)
6. Chronic opioid use (taking opioids for longer than 3 months)
7. Contraindication to general anesthesia, interscalene or superior trunk block
8. Herniated Cervical Disk, Cervical Myelopathy
9. BMI >35
10. Non English speakers

6.4 Randomization

The randomization will occur upon IRB approval and prior to start of study enrollment. Randomization will be revealed to the anesthesiologist after the patient gives consent in the holding area prior to surgery. After consent is obtained, the anesthesiologist will be given a sealed opaque envelope corresponding to the patients study ID number and randomization to either treatment or control. The envelope will be opened in the operating room, not in the presence of the investigators that assess the patients post-operatively

7.0 PROCEDURES

7.1 Surgical Procedure

Arthroscopic shoulder surgery

7.2 Data Collection

- Our primary outcome will be the incidence of hemidiaphragmatic paralysis (HDP) with superior trunk block and interscalene blocks as measured by ultrasound before and after the surgery as well as NRS Pain scores at rest in the PACU measured after the surgery every 30 minutes where worst pain in PACU will be the highest recorded number during PACU stay.
- Full resolution of the block will be reported by the patient on POD 1 via RA phone call
- Handgrip as measured by dynamometer. Maximum grip strength will be assessed pre op and upon 60 min after PACU arrival (2 measurements will be done per time point and the average will be recorded)
- Change in respiratory function as measured by changes in average minute ventilation, respiratory rate and tidal volume from preoperative baseline using a non-invasive monitoring device, and by changes in forced maneuvers: NIF, FEV1 and FVC measured preoperatively in holding area and 60 minutes postoperatively in the PACU.
- incidence of ISB related side effects: horner's syndrome, hoarseness, hiccups, coughing, dyspnea in PACU
- Time to readiness for PACU discharge (time of PACU admission to time of readiness to discharge, measured by Post Anesthetic Discharge Scoring System) evaluated every 15minutes.
- Block duration
- Incidence of paresthesia / neuropraxia (POD1, POD): persistent tingling, numbness in POD1, if patient reports persistent neuropraxia after POD2, will follow up on POD7. If persists, will notify attending anesthesiologist and continue to follow until postoperative neurologic symptoms (PONS) resolves.
- NRS Pain Scores at rest and with movement (PACU, POD 1, POD2)
- Opioid consumption (PACU, POD1, POD2)

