7.3 Schedule of Assessments

| Study Visit # | Surveys / Questionnaires | Randomization | Arthroscopic Shoulder Surgery | Ultrasound/Handgrip measurement/ Pulmonary Function Assessment |
|---------------------------|--------------------------|---------------|-------------------------------|---|
| Pre-op Holding Area | X | X | | X |
| Surgery | | | SOC | X |
| Post Anesthesia Care Unit | X | | | X |
| POD 1 | X | | | |
| POD 2 | X | | | |

X= Research procedures

SOC= Standard of care (care you would receive if you were not participating in this study)

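### The PACU side-effect endpoint has no specified pre-operative reading and no new-onset rule, so cough, dyspnea or hoarseness present before the block may dilute a secondary comparison that objective 4 depends on

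*Combined protocol and SAP*

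**What the plan says.** The endpoint reads "incidence of ISB related side effects: horner's syndrome, hoarseness, hiccups, coughing, dyspnea in PACU" in section 7.2 (Data Collection), section 5.2.2 (Secondary Endpoints) and the synopsis list of outcome parameters. The synopsis data-collection list names the same signs with no time point. None of these places gives a pre-operative reading or a condition that the sign be new since the block.

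The neighbouring endpoints do have a baseline. In section 7.2:

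- Lung function: "NIF, FEV1 and FVC measured preoperatively in holding area and 60 minutes postoperatively in the PACU".
- Handgrip: "Maximum grip strength will be assessed pre op and upon 60 min after PACU arrival".
- Diaphragm ultrasound is done before and after surgery.
- Minute ventilation, respiratory rate and tidal volume are expressed as change from a pre-operative baseline.

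Objective 4 in section 3.0 rests on one of the five signs: "Does the Superior trunk block spare the recurrent laryngeal nerve, preventing hoarseness more often than the ISB".

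Sections 6.2 and 6.3 admit ages 18 to 80 and ASA I to III. The only respiratory exclusion is "Patients with severe respiratory disease".

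Section 8.0 compares categorical secondary outcomes measured once by chi-square or Fisher's exact test, without adjustment.

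The schedule in section 7.3 has the row "Pre-op Holding Area | X | X | | X". Its first mark falls under surveys and questionnaires, and the content of that pre-operative survey is not given.

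**The concern.** An incidence attributed to a block needs some way of knowing that the sign was not there before. A patient with a mild chronic cough, some breathlessness or a hoarse voice meets the eligibility criteria. If that patient is assessed only in PACU, the sign can be recorded as a side effect of whichever block was given, and the unadjusted test has no means of removing it.

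Such patients are expected in equal proportion in both arms. They add the same background to each, which shrinks the contrast and raises both reported rates. A real sparing of the recurrent laryngeal nerve would be harder to detect, and the reported rates would mix old signs with new ones. The problem is plausible mainly for cough, dyspnea and hoarseness; Horner's syndrome and hiccups are less likely to pre-date the block. A baseline that is not taken before the block cannot be reliably reconstructed afterwards.

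**Working it through.** **The plan's own figure.** Inputs from section 8.0: margin 1.6, SD 2.9, alpha 0.025 (taken as one-sided), power 80%.

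n per group = 2 × 2.9² × (1.960 + 0.842)² / 1.6² = 51.6, so 52. This matches the plan. Then 52 × 1.2 = 62.4, rounded up to 63 per arm, gives the stated 126. The side-effect endpoint plays no part in this calculation.

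**Dilution model.** Let b be the share of patients with the sign before the block, and p the block-induced rate among the rest. Assume that pre-existing signs persist into PACU and are counted. Then:

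- Observed rate = b + (1 − b)p.
- Observed risk difference = (1 − b)(p₁ − p₂).
- If p₁ = p₂, the observed rates are also equal, so type I error is unaffected.

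**Assumed inputs.** The documents give neither p nor b. The illustration takes p = 20% vs 5%, n = 63 per arm and two-sided 0.05 (the same critical value as one-sided 0.025).

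Power = Φ[(d − 1.96·SE₀)/SE₁], where d is the observed risk difference, SE₀ uses the pooled rate and SE₁ the separate rates.

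- b = 0: d = 0.15, SE₀ = 0.0589, SE₁ = 0.0574. Power = Φ(0.601) = 73%.
- b = 10%: observed rates 28.0% vs 14.5%, d = 0.135, SE₀ = 0.0729, SE₁ = 0.0719. Power = Φ(−0.109) = 46%.

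For scoring of new signs only, the rates stay at 20% vs 5% and n becomes 63(1 − b).

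| b | Observed rates | Risk difference (points) | Risk ratio | Power, all PACU signs counted | Power, new signs only |
|---|---|---|---|---|---|
| 0 | 20.0% vs 5.0% | 15.0 | 4.0 | 73% | 73% |
| 1% | 20.8% vs 6.0% | 14.9 | 3.5 | 69% | 72% |
| 2% | 21.6% vs 6.9% | 14.7 | 3.1 | 66% | 72% |
| 5% | 24.0% vs 9.8% | 14.3 | 2.5 | 57% | 70% |
| 10% | 28.0% vs 14.5% | 13.5 | 1.9 | 46% | 68% |
| 20% | 36.0% vs 24.0% | 12.0 | 1.5 | 31% | 63% |

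**Sensitivity to the assumptions** (power with all PACU signs counted, against new signs only):

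- 40% vs 10%, 63 per arm: 97.0% against 97.8% at b = 2%; 95% against 97% at 5%; 91% against 97% at 10%.
- 30% vs 10%, with the 52 per arm that the plan expects to evaluate: 69% against 72% at b = 2%; 62% against 71% at 5%; 53% against 68% at 10%. Power with no pre-existing signs is 73%.

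The risk difference always shrinks by exactly the factor (1 − b). The risk ratio and the power fall faster, most of all when the lower rate is small.

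**The case against.** The strongest reply is that the protocol does not tell anyone to count old signs. The endpoint speaks of incidence and of effects related to the block, and both words imply new onset. A reader might infer that the plan scores every hoarse voice in PACU as a block effect. The text does not support that. What it lacks is the operational rule, and the reading on which to base one.

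A reader might also infer that no pre-operative reading will be taken. The documents do not establish this either. Section 7.3 schedules a holding-area survey of unstated content, so a symptom question is neither specified nor ruled out. Even if it is asked, nothing links the answer to the endpoint.

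A third tempting inference is bias. Randomization balances pre-existing signs in expectation, so neither block is favoured and type I error is not inflated.

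Finally, the size is entirely assumed. At 1 to 2% prevalence the loss against scoring new signs only is about 3 to 6 points at 20% vs 5%, and under 1 point at 40% vs 10%. Nothing in the documents supports a high baseline prevalence of hoarseness, the sign that objective 4 concerns. The endpoint is secondary and appears in none of the hypotheses in section 4.0.

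All of this limits the point. It does not remove the gap: there is no specified baseline and no new-onset rule for an endpoint that an objective relies on.

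**Conclusion.** The concern holds in limited form. As written, the side-effect endpoint cannot separate signs that pre-date the block from signs that follow it, and the planned test does not adjust for this. The consequence is dilution of a secondary comparison and inflated rates in both arms. The primary endpoints and the sample size are unaffected.

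Under the assumed 20% vs 5% with 63 per arm, the loss relative to counting only new signs is about 3 points of power at 1% prevalence, 6 at 2%, 13 at 5% and 22 at 10%. These figures illustrate a range and do not estimate this trial's loss: they depend on unseen rates and prevalence, and on pre-existing signs actually being counted. The case for acting is that the change is cheap and the baseline has to be taken before the block. It is a worthwhile improvement, not a threat to the trial's main conclusions.

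**What to change.** Add hoarseness, cough, dyspnea, hiccups and Horner's syndrome as five yes/no items to the holding-area survey in section 7.3, completed before the envelope is opened in the operating room (section 6.4). If the survey already asks about them, say so.

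In sections 5.2.2 and 7.2 and the synopsis, define each endpoint as present in PACU and absent pre-operatively. In section 8.0, state that patients positive at baseline for a sign are left out of that sign's denominator, or that the comparison is adjusted for baseline status. Because this status is recorded before allocation is revealed, either approach keeps the comparison randomized.

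The cost is five items at an existing visit and a few lines of text. Denominators become slightly smaller: at 10% prevalence, 63 × 0.9 = 56.7 per arm. The change does not separate block effects from those of the general anesthesia planned for every patient. Renaming the endpoint so that it does not refer to one arm's block is optional wording.

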7.3 Schedule of Assessments

| Study Visit # | Surveys / Questionnaires | Randomization | Arthroscopic Shoulder Surgery | Ultrasound/Handgrip measurement/ Pulmonary Function Assessment |
|---------------------------|--------------------------|---------------|-------------------------------|---|
| Pre-op Holding Area | X | X | | X |
| Surgery | | | SOC | X |
| Post Anesthesia Care Unit | X | | | X |
| POD 1 | X | | | |
| POD 2 | X | | | |

X= Research procedures

SOC= Standard of care (care you would receive if you were not participating in this study)

9.0 ADVERSE EVENT ASSESSMENT

All Adverse Events (AEs) will be reported in the final study report. Definitions for Adverse Event (AE) used in this study are listed below and are based on FDA and international guidelines:

9.1 Adverse Event (AE)

Patients will be made aware of the potential risks and study medications before enrollment. We will not enroll any patients with a history of adverse reactions to any of the study medications or are uncomfortable with study procedures. Once enrolled, if there is a physical risk, therapy will be initiated in the hospital, and patients will be monitored per standard of care by the hospital staff.

The anesthetic and surgical methods applied in the study are well documented and practiced for Shoulder Arthroscopy. The combination of these methods may increase the anticipated benefits by lowering patients' chances of hemidiaphragmatic paralysis and its side effects. Further, it may also spare hand grip. As a result, this may increase patient satisfaction post surgery.

9.2 Serious Adverse Events (SAE)

If a patient experiences complications, they will be kept at HSS for observation and withdrawn from the study. Such complications that would cause safety and toxicity concerns include local anesthetic toxicity, cardiac toxicity, and central nervous toxicity.

9.3 Subsequent Surgical Interventions Definitions

N/A

9.4 Adverse Event Reporting

The study will be monitored by the study investigators for adverse events. Any adverse events will be reported to the Institutional Review Board.

10.0 INVESTIGATOR RESPONSIBILITIES, RECORD AND REPORTS

10.1 Subject Consent and Information

Written/signed consent will be collected from participants in the holding area before surgery.

10.2 Subject Data Protection

- HSS tries to minimize those risks by (i) removing some direct identifiers from information stored [(i.e., names, social security numbers, medical record numbers)]; (ii) securing, in a

separate location, and limiting access to information linking codes (i.e., linkage codes) assigned to the registry information with direct participant identifiers; and (iii) limiting access to information stored to HSS investigators.

- Access to the REDCap program is password-protected, and access to a specific study's information within the program is limited to the research assistant and other IRB-approved study personnel who have been given permission to view and/or enter study data. REDCap program access is authorized by the CTSC; particular study access is granted by the research assistant. For data exports, fields marked as protected health information (PHI) in REDCap will be de-identified, if feasible.
- All transmission of data will occur via encrypted networks in password-protected files. Any paper-based data sheets utilized for the study will have personal identifiers removed whenever possible and will be stored in the department's locked office. Each subject will be assigned a unique study number for identification, and that number will not be derived from or related to information about the individual. Presentations and publications that result from this study will not contain any individual identifiers (at most the unique study numbers may be referred to). Thus our research presents a minimal risk of harm to subjects' privacy.
